### **8.6.2 Sample size**

In countries where Cerdelga will be available on the market at least 100 Cerdelga patients will be recruited in the study and approximately 50 Cerezyme patients will be included in the control group of safety sub-registry to descriptively compare the safety profile of Cerdelga to that of Cerezyme.

## **8.7 DATA MANAGEMENT**

### **8.7.1 Data collection schedule**

Data will be collected from enrolled patients by participating HCPs at the time of all patient office visits occurring as per local practice visit schedule or following the recommended schedule of assessments of the ICGG Gaucher Registry. Adverse events should be collected from patients at least every 6 months. If the period of time between the last ELISAFE sub-registry assessment and the next planned ICGG Gaucher Registry assessment is expected to be more than 6 months, a phone call to inquire about new/ongoing AEs is recommended.

If a patient temporarily stops (for any reason) treatment with Cerdelga or Cerezyme and the treating physician considers that the treatment can be potentially restarted, the patient can stay in the sub-registry as long as the sub-registry is open, the patient is willing to participate and is available for follow-up assessments. Collection of all AEs will be continued for the duration of 30 days after stopping Cerdelga or Cerezyme, and after that period only new SAEs will be collected and follow-up of ongoing AEs will be performed. Collection of all AEs in ELISAFE will be resumed when the patient restarts treatment with Cerdelga or Cerezyme.

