As the sub-registry is a voluntary program, the total number of patients who will participate and the total number of person-years of follow-up are not pre-defined, as not all patients have been identified, nor will all patients who could meet the study criteria may wish to participate. The sub-registry database has been designed to collect a variety of baseline and follow-up data obtained through routine clinical and laboratory assessments in the ICGG Gaucher Registry database. Each participating HCP is solely responsible for determining the appropriate clinical care for each patient. All data submissions are voluntary and there are no pre-determined follow-up periods. Participating sites will be encouraged to enter comprehensive baseline data at patient enrollment and to perform follow-up assessments at regular intervals, as described in the Recommended Schedule of Assessments of the ICGG Gaucher Registry. However, since this is a registry where data will be derived from routine clinical practice and not an interventional study, there will be no predefined diagnostic or monitoring procedures. Health Care Providers will decide what assessments to perform and when for each patient. Interviews, questionnaires and blood samples will be performed as in routine clinical practice.

In the sub-registry HCP's will be instructed to collect and report all AEs that occur during sub-registry participation, regardless of relationship to treatment.

The aim is to enroll as many patients on Cerdelga as possible.

Therefore, the only inclusion criteria for patients are:

- I 01. Male or female patient aged 18 years or older;
- I 02. The patient must be enrolled in the ICGG Gaucher Registry prior to safety sub-registry enrollment;
- I 03. The patient is willing and able to provide written informed consent for the safety sub-registry;
- I 04. The patient must have a confirmed diagnosis of GD, as defined in the protocol of the ICGG Gaucher Registry (documented acid  $\beta$ -glucosidase deficiency and/or mutations in the acid  $\beta$ -glucosidase gene);
- I 05. The patient must either initiate or continue treatment with Cerdelga or Cerezyme at the time of safety sub-registry enrollment.

The only exclusion criteria for patients are:

- E 01. The patient is concurrently enrolled in another clinical study; or participates in the compassionate use program with Cerdelga.

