### **8.3 VARIABLES**

The main analysis of interest will be the incidence rate of any AE report for Cerdelga-treated patients during participation in the sub-registry.

The outcome variable will be a report of an AE, exposure will be duration (in months or years) of time of exposure to Cerdelga while enrolled in the sub-registry, grouping factors will include category of Treatment Status (defined below), duration of GD treatment (including Cerdelga or other GD treatments) prior to enrolling in the sub-registry, selected demographic and baseline characteristics such as age, sex, and genotype as listed in [Section 8.7.5](#).

Category of treatment status at the time of sub-registry enrollment will be defined as:

- a) Patients naive to any GD treatment (ERT or SRT). This category will include, for example, newly diagnosed patients.
- b) Patients naive to the product of interest (Cerdelga in the Cerdelga group and Cerezyme in the comparator group) but experienced to any other treatment for GD (ERT or SRT). This category will include, for example, patients who will switch from any one therapy to the product of interest.
- c) Patients experienced to the treatment of interest. This category will include patients who were on treatment with the product of interest at entry into the sub-registry and then continue this therapy.

Note:

- Patients whose first GD treatment is commercial Cerdelga or Cerezyme, and who enroll in the sub-registry within 3 months of the first dose will be considered treatment naive for the purposes of analysis. Regardless of prior treatment, these patients must receive either Cerdelga or Cerezyme during their participation in the sub-registry.
- Previous exposure to Cerdelga in clinical studies will be considered for any patient of the sub-registry, notwithstanding the group of treatment they belong to during sub-registry participation.
- The data for enrolled patients who switch treatment from the Cerdelga to the Cerezyme or vice-versa during follow-up will be evaluated to and from the point of switch in the therapy.

- A subset of treatment experienced patients will be patients who will switch from any one therapy to any other therapy.
- When available, AEs reported by the patient and in the opinion of investigator related to Cerdelga intake and Cerezyme administration (prior to enrollment into the safety sub-registry) will be collected as part of the patient enrollment characteristics (medical history).

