### **8.7.5 Patient data**

Note: The observational study operates under real-world clinical practice conditions. It collects only available data. There are no imposed protocol visits or procedures.

Evaluation	At enrollment	Study follow-up assessments a,c	End of study
Informed Consent Form	x		
Inclusion criteria/Exclusion criteria	x		
Demographics *	x		
CYP2D6 predicted phenotype*	x		
GD history*	x		
Clinically significant medical history with assessment of relationship to Cerdelga or Cerezyme before enrollment	x		
GD treatment history*	x		
Current GD treatment*	x b	x b	x b
All adverse events		x	x
Concomitant medications for particular cases only d	x	x	x

\* Information collected as a part of ICGG Gaucher registry assessments

- a Frequency of the follow-up visits will be as per local practice visit schedule, or following the recommended schedule of events of the ICGG Gaucher Registry. Study assessments will be performed during office visits. In exceptional cases, follow-up information (including treatment status and AEs) could be collected by phone. Adverse events should be collected from patients at least every 6 months. If the period of time between the last ELISAFE sub-registry assessment and the next planned ICGG Gaucher Registry assessment is expected to be more than 6 months, a phone call to inquire about new/ongoing AEs is recommended.
- b Any data that are already entered in the ICGG Gaucher registry will not need to be entered in the sub-registry.
- c If a patient temporarily stops (for any reason) treatment with Cerdelga or Cerezyme and the treating physician considers that the treatment can be potentially restarted, the patient can stay in the sub-registry as long as the sub-registry is open, the patient is willing to participate and is available for follow-up assessments. Collection of all AEs will be continued for the duration of 30 days after stopping Cerdelga or Cerezyme, and after that period only new SAEs will be collected and follow-up of ongoing AEs will be performed. Collection of all AEs in ELISAFE will be resumed when the patient restarts treatment with Cerdelga or Cerezyme.

- d* Any corrective treatment prescribed following the occurrence of an AE. Any concomitant medication that caused an overdose. In case of relationship of the AE/overdose/pregnancy to other concomitant medication.

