Data collected in the ICGG Gaucher Registry and sub-registry to be used in this study include:

Upon enrollment into the sub-registry:

- Demographics
  - Gender and date of birth
  - CYP2D6 genotype testing result and date of blood sample collection, if available
- GD history
  - GD diagnosis confirmation
  - Date of diagnosis
  - GD type
- Primary GD treatment history:
  - Date and type of first primary GD treatment
  - Date, dose and type of all past primary GD treatments
  - Start date and dose of Cerdelga or Cerezyme treatment at sub-registry enrollment
- Date of sub-registry enrollment
- Clinically significant medical history (including AEs reported by patient and in opinion of investigator related to Cerdelga intake and Cerezyme administration which occurred prior to enrollment into the safety sub-registry).

At follow-up visits:

No experimental intervention is involved. Participating patients will undergo clinical assessments and receive treatment for GD, as determined by their treating HCPs and using the ICGG Gaucher Registry Recommended Schedule of Assessments as a guideline.

At each follow-up visit the following will be collected:

- Dosing information: including Cerdelga or Cerezyme regimen at the time of follow-up and treatment interruptions for  $\geq 1$  month or regimen changes since last visit with reasons for treatment interruptions or regimen changes.
- Adverse events: information on all AEs ongoing and occurring since the last visit, regardless of seriousness or relationship to Cerdelga or Cerezyme. Adverse events should be collected from patients at least every 6 months. If the period of time between the last ELISAFE sub-registry assessment and the next planned ICGG Gaucher Registry assessment is expected to be more than 6 months, a phone call to inquire about new/ongoing AEs is recommended.

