### **10.1.3 Obligations of the Investigator regarding safety reporting**

#### **10.1.3.1 Adverse Events collection**

All AEs regardless of relationship to Cerdelga or Cerezyme, spanning from the signature of the informed consent form until the end of the collection period for each patient (the last follow-up assessment of the particular patient), are to be recorded **immediately** (within 24 hours of awareness) for SAE and within 30 days of awareness for non-serious AE on the corresponding page(s) of the paper CRF or e-CRF, as explained below.

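### AE person-time is not tied to the last AE enquiry, and no planned analysis shows whether enquiry frequency differs between the groups

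*Combined protocol and SAP*

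**What the plan says.** **When AEs are asked about.** Section 8.7.1 has data collected "at the time of all patient office visits occurring as per local practice visit schedule", or on the parent registry's recommended schedule. It then sets a minimum: "Adverse events should be collected from patients at least every 6 months". If the gap to the next parent-registry assessment is expected to be longer, "a phone call to inquire about new/ongoing AEs is recommended". Section 6.2 adds: "All data submissions are voluntary and there are no pre-determined follow-up periods".

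**What each enquiry covers.** Section 8.7.5 lists, for each follow-up visit, "information on all AEs ongoing and occurring since the last visit, regardless of seriousness or relationship to Cerdelga or Cerezyme".

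**When AE collection stops.** Section 10.1.3.1 runs it from consent "until the end of the collection period for each patient (the last follow-up assessment of the particular patient").

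**What the denominator is.** Section 8.3 states: "exposure will be duration (in months or years) of time of exposure to Cerdelga while enrolled in the sub-registry". No section ties the end of this time to an AE enquiry. Section 8.8 applies similar calculations to Cerezyme.

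**Where treatment information comes from.** The table in Section 8.7.5 marks current Gaucher treatment as a parent-registry item, and footnote b says: "Any data that are already entered in the ICGG Gaucher registry will not need to be entered in the sub-registry". The same section also lists dosing among the items collected at each follow-up visit.

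**How the rate is used.** The rate of any AE is the primary analysis (Section 8.8.1). Sections 7.1 and 8.4 add the Cerdelga/Cerezyme ratio with a 95% confidence interval, and Section 8.8 says the constant-rate assumption will be evaluated.

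**The concern.** A rate is interpretable when events and person-time are counted over the same window. Here the events stop at the last assessment, while the person-time is defined by enrolment and treatment. Any time on drug after the last AE enquiry adds to the denominator and can add little to the numerator.

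The second issue is that the interval between enquiries is only softly controlled. The 6-month rule is worded as *should*, and the call that supports it is a recommendation. Most non-serious events come to light through contact with the site and are recalled less well over long gaps, so the absolute rate depends partly on how often patients are contacted.

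If contact differed between products, the ratio would move without any difference in safety. If contact thinned as patients stabilised, the AE rate would appear to fall with time, which is the pattern that Section 8.10 already expects for other reasons. Stratifying by treatment status would not separate the two explanations. Section 8.10 discusses the decline of AEs over time, selection and dropout, but not unequal ascertainment.

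**Working it through.** **1. The plan's own figure.** Section 8.6.1 says that 100 patients give more than 95% probability of seeing at least one patient with an AE whose cumulative rate is 5%. Check: 1 − 0.95^100 = 0.994. The statement is correct. It does not involve person-time and does not bear on this point.

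**2. The two windows side by side.**
- Numerator: consent to the last follow-up assessment (Section 10.1.3.1). The opening of Section 10 says instead the end of the study as defined for each patient, but no section says which contact marks that end.
- Denominator: time on drug while enrolled (Section 8.3).
- Inside the numerator window, each enquiry looks back to the previous visit, so gaps between enquiries are nominally covered. Only the tail after the last enquiry is strictly uncovered.

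**3. Size of the tail.** Let T be the enquiry interval and F the follow-up. If person-time ends at a random point in an interval and there is no closing contact, the mean tail is T/2, a share (T/2)/F of person-time. F is 4 to 6.5 years, from the rationale for Amendment 04. T is an assumption: 6 months is the plan's minimum frequency, and 12 months represents a missed minimum.

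| T | F = 4 years (48 months) | F = 6.5 years (78 months) |
|---|---|---|
| 6 months | 3/48 = 6.3% | 3/78 = 3.8% |
| 12 months | 6/48 = 12.5% | 6/78 = 7.7% |

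The AE rate is too low by the same share if no event in the tail is reported. A patient followed for less than 4 years would have a larger share.

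**4. Effect of the tail on the ratio.** The observed ratio is the true ratio × (1 − tail on Cerdelga)/(1 − tail on Cerezyme). With equal intervals and equal follow-up the factors cancel, and the ratio of about 1.2 expected in Section 8.6.1 stays at 1.2. With unequal intervals, F = 4 years and a 3-month tail share of 1.5/48 = 3.1%:
- Cerdelga every 6 months, Cerezyme every 3: 1.2 × 0.9375/0.96875 = 1.16.
- Cerdelga every 12 months, Cerezyme every 3: 1.2 × 0.875/0.96875 = 1.08.

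**5. Recall loss between enquiries.** This is separate from the tail. As an illustration, let a share s of AEs always be captured, and let the rest be recalled with half-life h. The captured fraction is c(T) = s + (1 − s)(1 − e^(−λT))/(λT), with λ = ln 2/h. Take s from 0 to 0.5 and h from 3 to 12 months, all assumed.
- Cerdelga every 6 months, Cerezyme every 3. With s = 0 and h = 3: 1.2 × 0.541/0.721 = 0.90. With s = 0.5 and h = 12: 1.2 × 0.923/0.959 = 1.15.
- The reverse: 1.2 × 0.721/0.541 = 1.60, and 1.2 × 0.959/0.923 = 1.25.
- Equal intervals: the ratio stays at 1.2, but both rates fall, with capture at 6 months of 54% to 92%.

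The first two cases respect the 6-month minimum, so meeting it would not by itself make the groups comparable. Ending person-time at the last enquiry removes the tail in steps 3 and 4 but does nothing for this recall loss.

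**The case against.** The strongest reply is that the plan already has sensible safeguards. The 6-month minimum is stated more than once and is the same for both products. Section 6.2 encourages follow-up at regular intervals. Dosing and AEs are collected at the same follow-up visits, so a visit that updates treatment should also be an AE enquiry. The table in Section 8.7.5 has an AE collection point at the end of study, and Section 8.7.6 asks for efforts to re-contact patients who withdraw. Section 8.9.2 applies quality control to all active sites. Softer wording also suits a study that, by Section 8.7.5, imposes no visits or procedures.

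Most of this stands, and it rules out three stronger readings.

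- A reader might infer that AEs are found only when someone asks. Section 10.1.1 also counts symptoms the patient offers spontaneously, staff observations, examination findings and clinically significant laboratory abnormalities.
- A reader might infer that on-drug time does accrue from the parent registry while AE enquiry lapses. Footnote b only avoids double entry, and no section names the source of person-time. The documents allow this reading but do not establish it.
- A reader might infer that the ratio is a measure of contact frequency. That needs contact to differ by product, and the documents give no contact frequencies.

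What the safeguards do not do is define the end of AE person-time or show whether enquiry was equally frequent in the two groups. A closing contact at the end of study shortens the tail only for patients who have one.

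**Conclusion.** The point holds as a gap in the exposure definition and in the planned analyses. As written, on-drug time after the last AE enquiry can count as event-free and lower the AE rate. The size is about 4% to 12.5% of person-time, assuming intervals of 6 to 12 months, 4 to 6.5 years of follow-up, no closing contact and no events reported from the tail. With closing contacts it is smaller.

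The rate ratio is biased only if enquiry frequency differs between the groups. The calculations show that such a difference could mask or exaggerate an expected ratio of 1.2, in either direction, but every interval and recall value in them is assumed. It is therefore a risk that the plan cannot detect, not a demonstrated bias. The comparison is descriptive and the primary endpoint is the Cerdelga rate, so the change is worth making but its absence does not undermine the study.

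**What to change.** - **Sections 8.3 and 8.8:** count AE person-time, for both products, only up to the last recorded AE enquiry, whether a visit or a call and including those where no AE was reported. Count events in the rate over the same window, and list later reports separately. Name the data source for treatment dates.
- **Section 8.8:** report AE enquiries per person-year by product and treatment status beside the rates.
- **Section 8.8:** add a sensitivity rate ratio limited to patients or periods that meet the 6-month interval. This is needed because truncation does not correct recall loss between enquiries.
- **Section 8.10:** list unequal ascertainment as a limitation.

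The cost is slightly less person-time, some added analysis, and possibly a CRF field for enquiry dates. The CRF is not among the documents, and visit dates may already be captured. Section 5 gives Q2 2018 as the start of data collection, so a new field would not cover earlier enquiries and existing visit dates would have to serve. Making the 6-monthly call mandatory is optional: it would tighten ascertainment, but it sits less easily with a study that imposes no visits, and the changes above do not depend on it.

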#### **8.4 STATISTICAL ANALYSIS**

Adverse events, SAEs, and events of interests will be summarized by treatment group, and by the three categories of treatment status and treatment group using percentage and frequency. For abnormal laboratory results assessed as AEs (clinically significant abnormal laboratory results), reported values of laboratory results in the course of AE follow-up will be summarized descriptively, including mean, standard deviation (SD), median, minimum and maximum. Categorical or qualitative variables will be summarized using percentages and frequency distributions. Timing of CYP2D6 genotyping and prevalence of CYP2D6 predicted phenotypes and GD subtype among Cerdelga-treated patients will be summarized using percentages and frequency.

In addition, the 95% confidence interval of incidence rates will be provided by treatment group. The risk of any AE in the Cerdelga group compared to Cerezyme will be evaluated in terms of the risk ratio with associated 95% confidence interval.

Data will be analyzed as available, missing data will not be imputed. For all AEs summary statistics, frequencies, cumulative incidence, and incidence rates per person-time will be calculated as appropriate. All summaries will be descriptive; no formal hypothesis testing will be performed.

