Analysis of endpoint: The main analysis of interest will be the incidence rate of any AE report for Cerdelga-treated patients during their participation in the sub-registry, considering treatment status at sub-registry enrollment (if applicable). If sufficient data within each treatment status category are collected, incidence rates within treatment status category will be estimated. Similar calculations will be performed for the Cerezyme-treated patients. Summaries will also be presented for three categories of treatment status within each of the Cerdelga and Cerezyme groups (if applicable). The implicit assumption of constant incidence rates over time will be evaluated.

Data will be analyzed as available, missing data will not be imputed. All summaries will be descriptive; no formal hypothesis testing will be performed.

As a part of exploratory analysis, specific analyses of the potential risks in the RMP and any new safety concern that could arise from the sub-registry will be conducted.

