#### **8.8.2 Secondary analysis**

- Incidence rate of any SAE.

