#### **10.1.3.2 Adverse event reporting to MAH/MAH representative**

- **All AEs (serious and non-serious)**
  - Are to be transmitted to the MAH including an appropriate causality assessment in relation to Cerdelga or Cerezyme.
  - Per the ICGG Gaucher Registry protocol ADRs are expected to be reported directly to Global Pharmacovigilance (GPV). However, for patients who are enrolled in the sub-registry, AE reporting should be done only in the sub-registry database (AE CRF) and not directly to GPV. If a patient leaves the sub-registry and remains in the ICGG Gaucher registry, ADR reporting should resume per the ICGG Gaucher Registry protocol.

- **In the case of an SAE** the Investigator must immediately:
  - ENTER (within 24 hours) the information related to the SAE in the appropriate screens of the e-CRF; the system will automatically send the notification to the MAH after approval of the Investigator within the e-CRF or automatically after a pre-set delay.
  - Copies of medical records for certain cases may be requested by the Sponsor. In such case, SEND (preferably by fax or e-mail) the photocopy of all examinations carried out and the dates on which these examinations were performed to MAH's GPV:

Global Pharmacovigilance
Fax: [name]
Email: [contact]

- Care should be taken to ensure that the patient's identity is protected and the patient's identifiers in the Study are properly mentioned on any copy of source document provided to MAH/MAH representative. For laboratory results, include the laboratory normal ranges.
- All further data updates should be recorded in the e-CRF as appropriate, and further requested documentation should be sent (by fax or e-mail) to MAH/MAH representative within 24 hours of knowledge. In addition, any effort should be made to further document each SAE that is fatal or life threatening within the week (7 days) following initial notification.

A back-up plan is used (using paper flow) in case the e-CRF system does not work.

- **In case of Non-Serious AEs**
  - ENTER (within 30 days) the information related to the AE in the appropriate screens of the e-CRF; the system will automatically send the notification to MAH/MAH representative after approval of the Investigator within the e-CRF or automatically after a pre-set delay.

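### The any-AE and SAE incidence rates have no single at-risk window: events follow participation, exposure is time on Cerdelga, and AE collection rules conflict after day 30 of a temporary stop

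*Combined protocol and SAP*

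**What the plan says.** - **Events.** Section 8.8 makes the main analysis the "incidence rate of any AE report for Cerdelga-treated patients during their participation in the sub-registry". The Abstract and Section 8.2.3 say the same. No on-treatment restriction is stated.
- **Exposure.** Section 8.3 says "exposure will be duration (in months or years) of time of exposure to Cerdelga while enrolled in the sub-registry". Nothing equivalent is defined for Cerezyme, although Section 7.1 plans a ratio of incidence rates and Section 8.4 a confidence interval for it.
- **Person-time.** Section 8.4 says only that "incidence rates per person-time will be calculated as appropriate".
- **Secondary rate.** Section 8.8.2 lists "Incidence rate of any SAE", with no window or denominator of its own.
- **Collection during a temporary stop.** Under Section 8.7.1 the patient may stay enrolled. All AEs are collected for 30 days, "after that period only new SAEs will be collected and follow-up of ongoing AEs will be performed", and full collection resumes on restart. The Abstract (Data Sources) and footnote c of Section 8.7.5 repeat this.
- **Collection in the safety chapter.** Section 10.1.3.1 asks for all AEs "spanning from the signature of the informed consent form until the end of the collection period for each patient", which it explains as the last follow-up assessment. Section 10 is similar. Neither mentions temporary stops.
- **Route.** For enrolled patients, Section 10.1.3.2 says "AE reporting should be done only in the sub-registry database (AE CRF) and not directly to GPV".

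**The concern.** A rate per person-time is interpretable only if every counted event falls in counted time, and all counted time could have produced a counted event. During a temporary stop the plan can fail on either side.

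If the denominator is time on drug, AEs from the first 30 days off drug and SAEs from any later point enter the numerator with no time behind them. If the denominator is participation time, the period after day 30 adds time but, under Section 8.7.1, no new non-serious events. Sites that follow Section 10 instead would add those events, so the numerator could also vary by site.

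These are the primary and secondary results of a post-authorisation safety study. Interruption may differ between an oral drug and the comparator, which would carry the error into the planned ratio. An open denominator also leaves the choice until after the data are seen.

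**Working it through.** **The plan's own figure.** The plan gives no figure on this point. Its one probability statement, in Section 8.6.1, reproduces: 1 − 0.95^100 = 0.994, which is more than 95%. This point does not affect it.

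**Where the collection rules agree and conflict.** Sections 8.7.1 and 10/10.1.3.1 agree on time on drug, on the first 30 days of a temporary stop, and on SAEs throughout. They conflict only for new non-serious AEs after day 30 of a temporary stop.

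**Inputs.**
- From the protocol: the 30-day period (8.7.1) and the expected ratio of 1.2 (8.6.1).
- Assumed, not in the protocol: off-drug share of participation f = 2% to 20%; serious share of AEs s = 5% to 20%; participation T = 4 years; one interruption per patient; every report counted; equal event rates on and off drug.
- Over 4 years (1,461 days), f = 2%, 5%, 10% and 20% means 29, 73, 146 and 292 days off drug.

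**Formulas.** On-drug time = (1 − f)T. Off-drug time = fT, of which the first w = 30/365.25 = 0.082 years has full collection and the rest is late.
- All events over on-drug time: factor = 1/(1 − f). This applies to SAEs, and to any AE if sites follow Section 10.
- Any AE under 8.7.1: N = on + min(off, w) + s × late. The factor is N/on with on-drug time, or N/T with participation time.

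**Example, f = 10%, s = 10%.** On = 3.6, first 30 days = 0.082, late = 0.318. N = 3.6 + 0.082 + 0.032 = 3.714. Then 3.714/3.6 = 1.032 and 3.714/4 = 0.928.

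| f | SAE, on-drug time | Any AE (8.7.1), on-drug time | Any AE (8.7.1), participation time |
|---|---|---|---|
| 2% | 1.020 | 1.020 | 1.000 |
| 5% | 1.053 | 1.023–1.028 | 0.972–0.976 |
| 10% | 1.111 | 1.027–1.040 | 0.925–0.936 |
| 20% | 1.250 | 1.037–1.071 | 0.830–0.856 |

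Ranges run over s = 5% to 20%. The any-AE error changes sign with the denominator. Over participation time the SAE factor is 1.00, because SAEs are collected throughout.

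**Ratio.** With all events over on-drug time, the ratio becomes 1.2 × (1 − f for Cerezyme)/(1 − f for Cerdelga).
- Equal shares: 1.20.
- Cerdelga 10%, Cerezyme 2%: 1.2 × 0.98/0.90 = 1.31.
- The reverse: 1.2 × 0.90/0.98 = 1.10.

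Under 8.7.1 collection with s = 10%, Cerdelga 10% and Cerezyme 2% give 1.2 × 1.032/1.020 = 1.21 with on-drug time, and 1.2 × 0.928/1.000 = 1.11 with participation time.

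**After the fix.** With the same window for events and time, the factor is 1.00 by construction. Adding 30 days to the denominator while still counting later SAEs is not enough. The any-AE factor is then 1.000 to 1.044, and at f = 20% the SAE factor is 4/(3.2 + 0.082) = 1.22.

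**The case against.** The strongest reply is that the effect may be negligible. Section 8.2.1 ties participation to receiving one of the drugs, with temporary stops as the exception, and Section 6.2 assumes long-term maintenance therapy. No interruption frequency is given. At 2% off drug the any-AE rate moves by 2% or not at all. All summaries are descriptive. Random error is also large: at an assumed 0.1 SAEs per patient-year over 400 patient-years (100 patients × 4 years), 40 SAEs carry a Poisson 95% interval of about −29% to +36%, wider than the largest shift above. This stands and limits the severity. It does not remove the point, because that interval does not cover a systematic mismatch.

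On collection, the temporary-stop rule was added deliberately (Annex 4, Amended protocol 01) and appears three times. It can fairly be read as a specific exception to a general rule. However, the safety chapter states its rule without that exception.

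A reader might infer more than the documents support:
- **That the plan divides by time on drug, so the rates are biased.** The on-drug denominator is an inference from Section 8.3. Section 8.4 leaves it open, and no bias of known size or sign is shown.
- **That the sections give opposite rules, which also affects the SAE rate.** The conflict is confined to new non-serious AEs after day 30. SAE collection agrees.
- **That events before first dose distort the rates.** Patients enroll after the treatment decision and must initiate or continue treatment at enrollment, so the gap is probably short.
- **That cutting switchers' data at the switch is an error.** The 30 days is a collection period, not an attribution rule. A carry-over analysis would be a preference.
- **That non-serious ADRs late in an interruption have no reporting route.** That follows only if Section 8.7.1 prevails over Section 10.

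**Conclusion.** The point holds as an inconsistency that should be fixed, not as demonstrated bias. Events are tied to participation, the only defined exposure is time on Cerdelga, no exposure is defined for Cerezyme, and the person-time is left open. Neither on-drug time nor participation time matches the any-AE numerator that Section 8.7.1 produces.

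The SAE rate is the more exposed if on-drug time is used: about 5%, 11% or 25% too high at 5%, 10% or 20% off drug. The any-AE rate under Section 8.7.1 is about 2% to 7% too high with on-drug time over 2% to 20% off drug, or up to 14% to 17% too low with participation time at 20%. The ratio is unaffected if interruption is equal in both groups. The shifts to 1.31 and 1.10 need unequal shares and all events divided by on-drug time.

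Every off-drug share, the serious share and the equal event rates on and off drug are assumptions. If SAEs themselves cause interruptions, the figures would differ.

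**What to change.** 1. In Sections 8.3, 8.4 and 8.8, define one on-treatment window per product. It opens at enrollment, or at first dose if later, and closes at the earlier of last dose + 30 days and first dose of the other product. It reopens on restart. The 30 days is the protocol's own period of full collection, so the window holds however the collection conflict is settled.
2. Use this window for both events and person-time, in both groups, for the any-AE rate, the SAE rate and their ratio. This also supplies the missing Cerezyme exposure definition.
3. List SAEs outside the window separately.
4. Reconcile Section 8.7.1, Section 8.7.5 and the Abstract with Sections 10 and 10.1.3.1 on AE collection off drug, and state where non-serious ADRs during a long interruption are reported.

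The cost is mainly wording. Section 8.7.5 records interruptions of at least 1 month with reasons but does not expressly list their dates, so the CRF should be checked for stop and restart dates. There are two small downsides. Late off-drug SAEs leave the rate, which is why they need their own listing. Interruptions under 1 month need not be recorded, but the 30-day extension absorbs nearly all of them.
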